8.1.1.1 Availability

Pinometostat is an investigational agent supplied to investigators by the Division of Cancer Treatment and Diagnosis (DCTD), NCI.

Pinometostat is provided to the NCI under a Collaborative Agreement between the Pharmaceutical Collaborator and the DCTD, NCI (see Section 13.4).

8.1.1.2 Agent Ordering and Agent Accountability

NCI-supplied agents may be requested by eligible participating Investigators (or their authorized designee) at each participating institution. The CTEP-assigned protocol number must be used for ordering all CTEP-supplied investigational agents. The eligible participating investigators at each participating institution must be registered with CTEP, DCTD through an annual submission of FDA Form 1572 (Statement of Investigator), NCI Biosketch, Agent Shipment Form, and Financial Disclosure Form (FDF). If there are several participating investigators at one institution, CTEP-supplied investigational agents for the study should be ordered under the name of one lead participating investigator at that institution.

In general, sites may order initial agent supplies when a subject is being screened for enrollment onto the study.

Submit agent requests through the PMB Online Agent Order Processing (OAOP) application. Access to OAOP requires the establishment of a CTEP Identity and Access Management (IAM) account and the maintenance of an “active” account status, a “current” password, and active person registration status. For questions about drug orders, transfers, returns, or accountability, call or email PMB any time. Refer to the PMB’s website for specific policies and guidelines related to agent management.

8.1.1.3 Agent Inventory Records

The investigator, or a responsible party designated by the investigator, must maintain a careful record of the receipt, dispensing and final disposition of all agents received from the PMB using the appropriate NCI Investigational Agent (Drug) Accountability Record (DARF) available on the CTEP forms page. Store and maintain separate NCI Investigational Agent Accountability Records for each agent, strength, formulation and ordering investigator on this protocol.

8.1.1.4 Investigator Brochure Availability

The current versions of the IBs for the agents will be accessible to site investigators and research staff through the PMB OAOP application. Access to OAOP requires the establishment of a CTEP IAM account and the maintenance of an “active” account status, a “current” password and active person registration status. Questions about IB access may be directed to the PMB IB Coordinator via email.

8.2 Commercial Agents

8.2.1 Cytarabine

Product description: Cytarabine Injection, an antineoplastic, is a sterile solution of cytarabine for intravenous and subcutaneous use which contains no preservative and is available in 20 mg/mL (1000 mg/50 mL) Pharmacy Bulk Package. Each mL contains 20 mg Cytarabine, USP and the following inactive ingredients: sodium chloride 0.68% and Water for Injection q.s. When necessary, the pH is adjusted with hydrochloric acid and/or sodium hydroxide to a target pH of 7.4. Each vial contains approximately 5.82 mEq sodium. Cytarabine is chemically 4-amino-1- β -Darabinofuranosyl- 2(1H)-pyrimidinone. Cytarabine is an odorless, white to off-white, crystalline powder which is freely soluble in water and slightly soluble in alcohol and in chloroform. Cytarabine Injection (non-preserved) can be administered by intravenous injection or infusion, subcutaneously, or intrathecally. Cytarabine is commercially available.

Solution preparation: A Pharmacy Bulk Package is a container of a sterile preparation for parenteral use that contains many single doses. The contents are intended for use in a pharmacy

admixture program and are restricted to the preparation of admixtures for intravenous infusion. Store the vial at 20°C to 25°C (68°F to 77°F). Do not refrigerate. Protect from light. Withdraw the desired dose into a syringe and further dilute in 250 to 1000 mL of 0.9% Sodium Chloride or D5W. Store the diluted product for administration at 20°C to 25°C (68°F to 77°F) and use within 24 hours.

Route of administration: Continuous intravenous infusion

Agent Ordering: Product is commercially available.

8.2.2 Daunorubicin

Product description: Daunorubicin hydrochloride is the hydrochloride salt of an anthracycline cytotoxic antibiotic produced by a strain of *Streptomyces coeruleorubidus*. It is provided as a deep red sterile liquid in vials for intravenous administration only. Each mL contains 5 mg daunorubicin (equivalent to 5.34 mg of daunorubicin hydrochloride), 9 mg sodium chloride; sodium hydroxide and/or hydrochloric acid (to adjust pH), and water for injection, q.s. It has the following structural formula which may be described with the chemical name of (1S,3S)-3-Acetyl-1,2,3,4,6,11-hexahydro-3,5,12-trihydroxy-10-methoxy-6,11-dioxo-1-naphthacenyl 3-amino-2,3,6-trideoxy- α -L-lyxo-hexopyranoside hydrochloride. Its molecular formula is C₂₇H₂₉NO₁₀•HCl with a molecular weight of 563.99. It is a hygroscopic crystalline powder. The pH of a 5 mg/mL aqueous solution is 4 to 5.

Solution preparation: The desired dose can be given as a slow IV push or is withdrawn into a syringe containing 10 mL to 15 mL of 0.9% Sodium Chloride Injection, USP Daunorubicin should not be administered mixed with other drugs or heparin. Store intact vials at 2°C to 8°C (36°F to 46°F). Protect from light. Retain in carton until time of use. Solution prepared for infusion in D5W or NS may be stored at 20°C to 25°C (68°F to 77°F) for up to 24 hours. Discard unused portion.

Route of administration: For IV administration only. Do not administer IM or SubQ. Dilute further into a total of 50-100 mL 0.9% (normal) saline and infuse over 10 to 30 minutes. Refer to the package insert for extravasation management.

Agent Ordering: Product is commercially available.

9. STATISTICAL CONSIDERATIONS

9.1 Study Design/Endpoints

This study is a multi-site phase 1b/2 study designed to confirm a safe and tolerable dose of pinometostat and to gauge preliminary evidence of efficacy when given as lead-in prior to and contemporaneous with standard intensive induction therapy for newly diagnosed AML with MLL rearrangement. The study design involves a brief safety run-in phase exploring two dosing

schemes, followed by a phase II efficacy expansion. The phase II expansion will use the higher dose-level of the two schedules if tolerated (see definitions below), otherwise, the lower dose-level if tolerated. The phase 1b/safety run-in portion will have a primary endpoint of dose limiting toxicity, while the phase 2 portion will have a primary endpoint of complete remission / complete remission with incomplete count recovery attainment, and will gather additional laboratory correlative data.

The phase 1b safety run-in phase involves dividing patients into two cohorts (cohort 1 and cohort 2) after appropriate screening. The goal will be to identify a maximum tolerated dose for expansion. Dose escalation will occur in the standard cohorts-of-3/3+3 design, which is described below. Cohort 1 will comprise of 3-6 patients and will be treated with pinometostat 90 mg/m² continuous IV infusion (CIVI) on days 1-7, then decrease dose to 60 mg/m² CIVI for days 8-35, along with daunorubicin 60 mg/m² daily on days 8-10 and cytarabine 100 mg/m² CIVI on days 8-14. Cohort 2 will comprise of 3-6 patients and will be treated with pinometostat 90 mg/m² CIVI on days 1-35, along with daunorubicin 60 mg/m² daily on days 8-10 and cytarabine 100 mg/m² CIVI on days 8-14.

Safety and tolerability evaluation and dose escalation for phase 1b will be performed in the usual 3+3 fashion. See Figure 1. Briefly, 3 patients will be enrolled on cohort 1. If zero of three patients experience dose-limiting toxicities (DLT) on pinometostat, proceed to enroll cohort 2. If one of three patients experience DLT, enroll an additional three patients for a total of six patients on cohort 1. If still only one of six total patients experience DLT, proceed to enroll cohort 2. If 2 or more (of either three total or six total patients) experience DLT, accrual will be stopped and a safety review and consideration of further dose level reductions will be discussed between PI, CTEP, and stakeholders. Cohort 2 will be evaluated likewise, except that no further dose level increases of pinometostat will be made, and if toxicity is unacceptable in cohort 2, the dosing plan of pinometostat for cohort 1 will move forward into the expansion phase. Otherwise, the dosing plan for cohort 2 will move forward into phase II expansion. The highest dose of pinometostat that is tolerated as described here will be considered the maximally tolerated dose (MTD).

[figure not shown]

Figure 1. A standard 3+3 dose escalation. With only two cohorts (dose levels), escalation stops

after cohort 2; if 2-3/3 DLT at dose level 1 (cohort 1), a safety review will be initiated to decide whether dose level reductions below the starting dose should be considered.

The phase 2 expansion phase will use the maximum tolerated dose/schedule as determined by phase 1b above and accrue additional patients to gather preliminary evidence of efficacy. Patients will be treated in the same manner as in the phase 1b portion above, with the exception that only a single dose level/cohort will be expanded.

The expansion cohort will comprise 4-25 patients who will be treated at the maximum tolerated dose schedule (see below; phase 1b patients who were treated at the MTD will be included in the statistical analysis of efficacy together with phase 2 patients, which in total comprises 10-31 patients).

Patients requiring re-induction, if any, will be treated at the assigned dose of pinometostat. Patients undergoing re-induction treatment will be analyzed jointly with patients not requiring re-induction for analysis of the primary efficacy endpoint, but a subgroup analysis consisting only of patients who did/did not require a second induction may be conducted.

The primary efficacy objective is to calculate the rate of complete response (CR) or complete response with incomplete count recovery (CRi) after combination treatment and the primary efficacy hypothesis is that the rate of CR will be higher than among historical controls.

H0: The CR rate is $\leq 65\%$

Ha: The CR rate is $\geq 85\%$

We will use a Simon two-stage design (minimax) to test the hypothesis that the CR rate is greater than 65%. Assuming that the true CR rate among those treated is at least 85%, and setting type I and type II error rates to 10% (yielding $\alpha=\beta=0.1$), we will enroll 13 patients in the first stage. If 8 or fewer responses are observed during stage 1, the study will be stopped early. If there are 9 or more responses, an additional 18 patients will be enrolled in stage 2 for a total of 31 patients. At the completion of the second stage, the drug will be declared efficacious and the probability of an unacceptable CR rate $\leq 64\%$ ruled out if at least 24 CRs are observed out of all 31 patients. This design has a 90% power to correctly rule out a CR rate $\leq 65\%$ if the true rate is 85%, with a type 1 error rate of 0.0951.

| | |
|-----------|----|
| N | 31 |
| n1 | 13 |
| r1 | 8 |
| n2 | 18 |
| r2 | 23 |

NOTE: Patients treated at the maximum tolerated dose in the phase 1b portion (3, or 6) will be counted toward the total needed to satisfy the statistical design. This means that possible total accrual ranges for the whole trial are not $[6, 12+31] = [6, 43]$ but $[6, 12 + 31 - 6] = [6, 37]$

For both phases, early response evaluation will occur at day 21 (day 14 of 7+3) with a bone marrow examination, and if $> 5\%$ myeloid blasts are seen, or $\leq 5\%$ myeloid blasts but with an

aberrant immunophenotype matching the pretreatment immunophenotype, a re-induction attempt may be made with 5 and 2 days of cytarabine and daunorubicin, respectively, both medications at the same doses as initial induction. Pinometostat will be given at 90 mg/m², unless 60 mg/m² was previously established as the RP2D, in which case it shall be given at 60 mg/m². The clock will be reset, and pinometostat will be administered for an additional 28 days (unless stopped early for reasons of toxicity, withdrawal from study, or death).

Exploratory pharmacodynamics biomarkers will be collected at screening, at day 8, and at relapse if applicable for both phases (these are described above).

Length of study treatments

Study treatment will end after either 35 days (first induction) or 28 days (with calendar reset to day 1 on the first day of 5+2 in second induction attempt) of pinometostat. Patients should then receive standard of care consolidative therapy including allogeneic bone marrow transplant, but these are not considered study treatments. No specific consolidation is mandated.

Follow-up period

Patients will be followed until the soonest of death, alternative leukemia therapy (i.e. for relapsed or refractory disease; this is excluding the planned consolidation that may directly follow the study treatment) initiated, enrollment on another therapeutic clinical trial, bone marrow transplantation, voluntary or involuntary withdrawal from study (see section 6.5) or lost to follow-up.

Toxicity assessment

All patients who receive any amount of the study drug will be evaluable for toxicity. Toxicity will be graded and reported according to the Common Terminology Criteria for Adverse Events (CTCAE) Version 5. The CTEP Active Version of the CTCAE is identified and located on the CTEP website at http://ctep.cancer.gov/protocolDevelopment/electronic_applications/ctc.htm. All appropriate treatment areas should have access to a copy of the CTEP Active Version of CTCAE.

It is recognized that drug-related toxicity in this population may be difficult to ascertain, given the aggressive hematologic disease. Investigators will attempt to assign attribution of toxicities to each drug if possible. Toxicity attributed to any of the three agents will be considered dose limiting. Dose limiting toxicity will be divided into non-hematologic and hematologic toxicity.

Dose-limiting toxicity

Definitions of dose-limiting toxicities are in section 6.2.

Patients who receive at least 1 dose of pinometostat during cycle 1 will be considered to be evaluable for toxicity/DLT and will not be replaced during the dose escalation phase of the trial unless the PI determines that further additional patients at that dose level are required for safety purposes; the context in which DLTs are noted (before or after the introduction of 7+3) will be considered in this decision. Patients with transient liver function test abnormalities (AST, ALT, bilirubin, or alkaline phosphatase) that resolve to < grade 1 within 5 days will not be considered DLT. Infection will not constitute DLT unless it is felt that the infection resulted from

unexpectedly complicated myelosuppression (degree or duration).

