9.2 Sample Size/Accrual Rate

The planned sample size for both the phase 1b/2 portions is between 6 and 37 patients, and the planned accrual rate is 1/month/site (4-6 monthly across ETCTN) based on data from similar trials completed by our organization during the previous 5 years.

PLANNED ENROLLMENT REPORT, PHASE 1b

| Racial Categories | Ethnic Categories | | | | Total |
|---|------------------------|----------|--------------------|----------|-----------|
| | Not Hispanic or Latino | | Hispanic or Latino | | |
| | Female | Male | Female | Male | |
| American Indian/ Alaska Native | 0 | 0 | 0 | 0 | 0 |
| Asian | 0 | 0 | 0 | 0 | 0 |
| Native Hawaiian or Other Pacific Islander | 0 | 0 | 0 | 0 | 0 |
| Black or African American | 1 | 1 | 0 | 0 | 2 |
| White | 4 | 4 | 1 | 1 | 10 |
| More Than One Race | 0 | 0 | 0 | 0 | 0 |
| Total | 5 | 5 | 1 | 1 | 12 |

PLANNED ENROLLMENT REPORT, PHASE 2

| Racial Categories | Ethnic Categories | | | | Total |
|---|------------------------|-----------|--------------------|----------|-----------|
| | Not Hispanic or Latino | | Hispanic or Latino | | |
| | Female | Male | Female | Male | |
| American Indian/ Alaska Native | 0 | 0 | 0 | 0 | 0 |
| Asian | 0 | 0 | 0 | 0 | 0 |
| Native Hawaiian or Other Pacific Islander | 0 | 0 | 0 | 0 | 0 |
| Black or African American | 2 | 2 | 0 | 0 | 4 |
| White | 8 | 10 | 1 | 2 | 21 |
| More Than One Race | 0 | 0 | 0 | 0 | 0 |
| Total | 10 | 12 | 1 | 2 | 25 |

PHS 398 / PHS 2590 (Rev. 08/12 Approved Through 8/31/2015)

OMB No. 0925-0001/0002

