13.1 Study Oversight

This protocol is monitored at several levels, as described in this section. The Protocol Principal Investigator is responsible for monitoring the conduct and progress of the clinical trial, including the ongoing review of accrual, patient-specific clinical and laboratory data, and routine and serious adverse events; reporting of expedited adverse events; and accumulation of reported adverse events from other trials testing the same drug(s). The Protocol Principal Investigator and statistician have access to the data at all times through the CTMS web-based reporting portal.

For the Phase 1 portion of this study, all decisions regarding dose escalation/expansion/de-escalation require sign-off by the Protocol Principal Investigator through the CTMS/IWRS. In addition, for the Phase 1 portion, the Protocol Principal Investigator will have at least monthly, or more frequently, conference calls with the Study Investigators and the CTEP Medical Officer(s) to review accrual, progress, and adverse events and unanticipated problems.

For a Phase 1/2 trial, enrollment to the Phase 2 portion of the trial will not begin until a protocol amendment has been submitted which summarizes the Phase 1 results, the recommended Phase 2 dose, and the rationale for selecting it. The amendment must be reviewed and approved by CTEP before enrollment to the Phase 2 portion can begin.

During the Phase 2 portion of the study, the Protocol Principal Investigator will have, at a minimum, quarterly conference calls with the Study Investigators and the CTEP Medical

Officer(s) to review accrual, progress, and pharmacovigilance. Decisions to proceed to the second stage of a Phase 2 trial will require sign-off by the Protocol Principal Investigator and the Protocol Statistician.

All Study Investigators at participating sites who register/enroll patients on a given protocol are responsible for timely submission of data via Medidata Rave and timely reporting of adverse events for that particular study. This includes timely review of data collected on the electronic CRFs submitted via Medidata Rave.

All studies are also reviewed in accordance with the enrolling institution's data safety monitoring plan.

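### The expansion size (4-25) and efficacy total (10-31) in section 9.1 do not match the 13/31 Simon design in the same section

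*Combined protocol and SAP*

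**What the plan says.** Section 9.1 of the combined protocol and SAP sizes the efficacy population twice.

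- The description of the expansion phase reads "The expansion cohort will comprise 4-25 patients who will be treated at the maximum tolerated dose schedule". It adds that phase 1b patients treated at the MTD join the efficacy analysis, "which in total comprises 10-31 patients".
- The hypothesis-test text sets a Simon minimax design for a CR rate of 65% against 85%, with 10% type I and type II error. It states "we will enroll 13 patients in the first stage", stops the study on 8 or fewer responses, and otherwise "an additional 18 patients will be enrolled in stage 2 for a total of 31 patients". Success requires that "at least 24 CRs are observed out of all 31 patients".
- The NOTE under the design table says "Patients treated at the maximum tolerated dose in the phase 1b portion (3, or 6) will be counted toward the total needed", and derives a whole-trial maximum of 12 + 31 - 6 = 37.

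Section 9.2 repeats the overall range: "The planned sample size for both the phase 1b/2 portions is between 6 and 37 patients". Its planned enrollment tables total 12 for phase 1b and 25 for phase 2.

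**The concern.** The two-stage rule has only two planned end points for efficacy: 13 patients if stage 1 fails, or 31 if it passes. A total of 10 corresponds to neither, and the plan gives no look or futility rule at 10. At the upper end, 25 expansion patients make 31 only when added to 6 from phase 1b, yet the NOTE also allows 3. Three at the MTD is an ordinary outcome: each cohort has 3 to 6 patients, and no DLT among the first 3 in cohort 2 takes that schedule into expansion.

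The practical risk lies with the figure 25, which also appears as the phase 2 total in the section 9.2 table and could be used as the accrual target. With 3 patients at the MTD, accrual would then end at 28. A success rule written for 31 patients could not be applied as designed, and the power of the primary efficacy test would no longer be the one stated.

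**Working it through.** **Inputs (section 9.1).** p0 = 0.65, p1 = 0.85; n1 = 13, r1 = 8 (stop if 8 or fewer respond); N = 31, r = 23 (success if 24 or more respond); m = 3 or 6 phase 1b patients at the MTD.

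**Step 1: reproduce the plan's design.** The probability of declaring success at true rate p is

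P(p) = Σ over x = 9 to 13 of Bin(x; 13, p) × Pr[Bin(18, p) ≥ 24 - x].

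- P(0.65) = 0.0951, the stated type I error.
- P(0.85) = 0.9036, the stated 90% power.
- Probability of stopping at stage 1 when p = 0.65: 0.499.

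A search over designs meeting both 10% targets returns the same minimax design. The design is sound.

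**Step 2: expansion sizes that the design implies.** Expansion = 13 - m if stopped at stage 1, and 31 - m if completed.

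| m at MTD | Stopped at stage 1 | Completed | 4 + m | 25 + m |
|---|---|---|---|---|
| 6 | 13 - 6 = 7 | 31 - 6 = 25 | 10 | 31 |
| 3 | 13 - 3 = 10 | 31 - 3 = 28 | 7 | 28 |

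The lower bound of 4 gives 10 or 7 efficacy patients, which is 3 or 6 short of stage 1. The upper bound of 25 gives 31 or 28, and 28 is 3 short of N. Both ends of the stated total equal the expansion figure plus 6, so the 3-patient case was left out.

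**Step 3: whole-trial totals.** With 3 or 6 patients at the dose not chosen, a completed trial has 31 + 3 = 34 or 31 + 6 = 37 patients. A trial stopped at stage 1 has 13 + 3 = 16 or 13 + 6 = 19. The maximum is the same for either m: 12 + 25 = 37 with m = 6, and 9 + 28 = 37 with m = 3.

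**Step 4: what happens at 28.** This applies only if 25 is enforced as a ceiling with m = 3. The stage 1 rule is kept (n1 = 13, r1 = 8) and N = 28, so stage 2 has 15 patients.

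| Success if at least | Type I error (p = 0.65) | Power (p = 0.85) |
|---|---|---|
| 24 of 28 | 0.0136 | 0.587 |
| 23 of 28 | 0.0390 | 0.762 |
| 22 of 28 | 0.0891 | 0.876 |
| 21 of 28 | 0.1665 | 0.933 |

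No cut-off meets both 10% targets. Over all stage 1 sizes (1 to 27), stopping rules and final cut-offs at N = 28, the highest power with type I error at or below 0.10 is 0.885. It is reached at 22 of 28 with effectively no early stop, where type I error is 0.0923. Re-setting the rule at 28 cannot recover 90%.

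**The case against.** The best defence is that the descriptive sentence refers the reader onward to the design text, which is complete and can be run as it stands. The expansion size follows from it by subtraction. The full efficacy size is 31 in both places, the maximum of 37 is right for either cohort size, and no decision rule hangs on 10. Nothing calls 25 a cap that overrides the Simon design, so the loss of power is hypothetical. Section 13.1 adds safeguards: "enrollment to the Phase 2 portion of the trial will not begin until a protocol amendment has been submitted", with CTEP approval, and the statistician must sign off before stage 2. The number treated at the MTD will be known by then. Section 9.1 also lets the principal investigator add patients at a dose level for safety, so a cohort need not be exactly 3 or 6.

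Most of this stands as a limit on the consequence. It does not remove the error. No text ranks one part of section 9.1 above the other, and 10 cannot be the planned end of the efficacy analysis. The required amendment covers phase 1 results and the choice of dose, not the sample-size text, so it offers an occasion for the correction without making it. The point about added patients is fair, and is why the replacement wording should lead with the general rule and give the four numbers as the cases that the NOTE names.

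**Conclusion.** The concern holds. The ranges 4-25 and 10-31 are wrong as written. The planned efficacy total is 13 or 31, and the expansion is 7 or 25 with 6 patients at the MTD, or 10 or 28 with 3. The Simon design, its error rates and the maximum of 37 are correct.

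If the design text is followed, power is 0.9036 and nothing is lost. If the 25 is enforced with 3 patients at the MTD, power falls to 0.587 under the rule of 24 responses, and to at most 0.885 under any rule that holds type I error at 10%. These figures assume exact binomial responses, the plan's rates of 65% and 85%, every enrolled patient counted in the analysis, and 3 or 6 patients at the MTD as the NOTE states. This should be fixed before phase 2 opens.

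**What to change.** - **Section 9.1, expansion size.** Replace 4-25 with: the expansion enrols the remainder needed to reach 13 efficacy patients at stage 1 and 31 in total, that is 7 (stopped at stage 1) or 25 (completed) if 6 phase 1b patients were treated at the MTD, and 10 or 28 if 3 were.
- **Section 9.1, efficacy total.** Replace 10-31 with: 13 if stopped at stage 1, or 31.
- **Section 9.2.** State that the phase 2 target of 25 goes with 6 patients at the MTD (phase 1b up to 12) and becomes 28 with 3 (phase 1b up to 9), with the maximum of 37 unchanged.
- **Secondary, with no bearing on the efficacy test.** The stated minimum of 6 for the whole trial is not strict, because accrual stops for a safety review if 2 or more of the first 3 patients have a DLT. Say that accrual can stop at 3 pending that review.

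The cost is wording only, and the change can go into the amendment already required before phase 2. No design parameter changes and no patients are added beyond the stated maximum.
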